3 STUDY OBJECTIVES AND ESTIMANDS

3.1 Objectives

A month is defined as 4 weeks (28 days) for the purpose of this protocol.

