6.2.6.1 Study Medication

Study drug is dispensed in a wallet-type blister card with a unique wallet number. Each wallet has 8 tablets. During the DBT Phase, each wallet contains only rimegepant or matching placebo depending on the randomization. During the OLE Phase, each wallet contains only rimegepant. The Investigational Product (IP) Administration – DB and OL CRFs collect the dosing date, number of tablets taken, and dosing day type (scheduled or non-scheduled), and wallet number (see Section 9.4).

The wallet type identifier associated with a wallet number is DB rimegepant, DB placebo, or OL rimegepant, and is obtained by merging the IP Administration CRF data with the external DB study drug wallet list file data and OL rimegepant wallet list file data by wallet number (i.e., kit number).

The by-subject listing of study drug is provided for the safety analysis set, and presents dosing date, study day derived from the dosing date, number of tablets taken, dosing day type (scheduled, non-scheduled) wallet number, and wallet type identifier. Records with number of tablets taken ≥ 0 are displayed for scheduled dosing days to account for missed doses. Records with number of tablets taken > 0 are displayed for non-scheduled dosing days. The listing also displays rimegepant exposure parameters (time on DBT, time on OL rimegepant, time on DB or OL rimegepant, DB study drug start end dates, and OL rimegepant start and end dates), and identifies invalid wallet numbers. Valid DB wallet numbers are those in the DB study drug wallet list file. Valid OL wallet numbers are those in the OL rimegepant wallet list file. The listing is sorted by site-subject ID, dosing date, day type, and wallet number.

DB Study Drug Exposure

DB study drug exposure is summarized descriptively by treatment group, and includes the following parameters:

- Time on DBT (weeks), derived as (DBT end date DBT start date + 1)/7
- Time on study drug categories: $< 2, \ge 2$ to $< 4, \ge 4$ to $< 8, \ge 8$ to $< 12, \ge 12$ weeks
- Cumulative DB exposure (tablets), derived by summing the number of tablets across records with complete dosing date and valid DB wallet number
- Average DB exposure (tablets per month), derived as (1) cumulative DB exposure if time on DB study drug < 14 days, or (2) 4 × cumulative DB exposure/time on DB study drug if time on DB study drug if time on DB study drug ≥ 14 days

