6.2.6.2 Measurements of Treatment Compliance

DB Treatment Compliance

The by-subject listing of DB treatment compliance is provided for the safety analysis set, and displays results for DB treatment compliance parameters in separate columns: average DB exposure (tablets per month; see Section 6.2.6.1); percentage for DB tablet count compliance and odd study drug dosing day compliance; flags for the other parameters ("Y" or missing).

The frequency table of DB treatment compliance is provided by treatment group for the safety analysis set, and displays the following categories:

- DB study drug taken but not randomized
- DB tablet count compliance ≥ 80% from DB study drug start to later of last scheduled DBT Phase visit or DB study drug end/OL rimegepant start. Tablet count compliance is derived as 100 × cumulative DB exposure/required cumulative DB exposure, where
 - Cumulative DB exposure is defined in Section 6.2.6.1.
 - Required cumulative DB exposure is derived as follows:
 - Let n = DB maxdate DB study drug start date + 1.
 - DB maxdate is defined as the latest of the (1) Week 2, 4, 8, and 12 visit dates from the Visit Date DB CRFs, (2) Week 52/EOT visit date from the Visit Date OL CRF, if it is in the DBT safety analysis period (see Section 7.2), and (3) DB study drug end date.
 - If DB maxdate \geq OL rimegepant start date, then DB maxdate is set to OL rimegepant start date -1 day.
 - If n is even, then the required cumulative DB exposure is n/2.
 - If n is odd, then the required cumulative DB exposure is n/2 + 1.
- Average DB exposure (tablets per month) categories:
 - \circ > 16.8 (> 20% above EOD dosing)
 - \circ > 15.4 (> 10% above EOD dosing)
 - $\circ \geq 12.6 \text{ to} \leq 15.4 \ (\pm 10\% \text{ of EOD dosing})$
 - $\circ \geq 11.2 \text{ to} \leq 16.8 (\pm 20\% \text{ of EOD dosing})$
 - $\circ \geq 12.6 (\geq 90\%$ compliant with EOD dosing)
 - $\circ \geq 11.2 (\geq 80\%$ compliant with EOD dosing)
Average exposure is defined in Section 6.2.6.1.

- DB tablets taken per month for 3 consecutive months categories: $\geq 12, \geq 13$, and ≥ 14

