 - Tablets per month are assessed by the number of 4-week (28-day) intervals in which a subject exceeded select tablet counts from the DB study drug start date to the DB study drug end date, where the number of 4-week intervals are consecutive (see Section 6.3.1.1 for months). For example, suppose a subject takes 20 tablets through 4 weeks, 10 tablets after 4 weeks to 8 weeks, and 25 tablets after 8 weeks to 12 weeks. Thus, this subject is not considered to have taken ≥ 14 tablets (more than EOD frequency) per month for 3 consecutive months.
- > 1 DB tablet taken on any 1 day
- ≥ 1 non-scheduled DB study drug dosing day (see Section 9.4)
- Incorrect DB study drug taken
 - All the time. Defined as as-treated treatment group not equal to as-randomized treatment group, i.e., any of the following:
 - Subjects randomized to rimegepant who took (1) ≥ 1 tablet from a DB placebo wallet, and (2) no tablets from a DB rimegepant wallet
 - Subjects randomized to placebo who took (1) ≥ 1 tablet from a DB rimegepant wallet, and (2) no tablets from a DB placebo wallet.
 - At least once. Defined as any of the following:
 - Subjects randomized to rimegpant who took ≥ 1 tablet from a DB placebo wallet
 - Subjects randomized to placebo who took ≥ 1 tablet from a DB rimegepant wallet.
- Time on study drug > 14 weeks.

Results for all categories are displayed, even those with 0 counts.

OL Rimegepant Treatment Compliance

The by-subject listing of OL rimegepant treatment compliance is provided for the safety analysis set, and displays results for OL rimegepant treatment compliance parameters in separate columns: average DB exposure (tablets per month; see Section 6.2.6.1); percentage for OL rimegepant tablet count compliance; flags for the other parameters ("Y" or missing).

The frequency table of OL rimegepant treatment compliance is provided by treatment group for the safety analysis set, and displays the following categories:

- OL rimegepant tablet count compliance ≥ 80% from OL rimegepant start to later of last scheduled OLE Phase visit or OL rimegepant end. Tablet count compliance is derived as 100 × cumulative OL rimegepant exposure/required cumulative OL rimegepant exposure, where
 - Cumulative OL rimegepant exposure is defined in Section 6.2.6.1.
 - Required cumulative OL rimegepant exposure is derived as follows:

- Let n = OL maxdate OL rimegepant start date + 1.

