7 CONVENTIONS

7.1 Derived Dates

Derived dates are defined as follows:

- Screening visit date: visit date from the Visit Date SS CRF with folder name "Screening Visit"
- eDiary efficacy date: complete datepart{eDiary finding date/time} 1 day from the eDiary headache report
- Study drug start date: earliest complete dose date from IP Administration DB or OL CRF with number of tablets taken > 0. This is an analysis period reference date.
- Study drug end date: latest complete dose date from IP Administration DB or OL CRF with number of tablets taken > 0
- Study drug last date:
 - Before the final database lock: study drug end date derived only for subjects who have either (1) or (2):
 - (1) "Yes" or "no" response to the phase completion question on the DB Subject Status CRF, and {either (1a) "no" response to the continuing to the next phase question on the DB Subject Status CRF, or (1b) "Follow-up" specified as the next phase on the DB Subject Status CRF}, and missing OL rimegepant start date
 - (2) "Yes" or "no" response to the phase completion question on the OLE Subject Status or Follow-up Subject Status CRF
 - Final database lock: study drug end date

This is an analysis period reference date.

- DB study drug start date: earliest complete dose date from IP Administration DB or OL CRF records with number of tablets taken > 0 and valid DB wallet number. This is an analysis period reference date.
- DB study drug end date: latest complete dose date from IP Administration DB or OL CRF records with number of tablets taken > 0 and valid DB wallet number
- DB study drug last date:
 - Before the first database lock: DB study drug end date derived only for subjects with "yes" or "no" response to the phase completion question on the DB Subject Status, OLE Subject Status, or Follow-up Subject Status CRF
 - First database lock or after: DB study drug end date

This is an analysis period reference date.

• OL rimegepant start date: earliest complete dose date from IP Administration – DB or OL CRF records with number of tablets taken > 0 and valid OL wallet number. This is an analysis period reference date.

- OL rimegepant end date: latest complete dose date from IP Administration DB or OL CRF records with number of tablets taken > 0 and valid OL wallet number
- OL rimegepant last date:

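### Below 14 days on double-blind drug, the SAP's monthly tablet figure is an unscaled count, so its every-other-day compliance bands misclassify both adherent and daily-dosing subjects

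*SAP*

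**What the plan says.** The SAP supplied is for the prevention study C4951021, and this point concerns that study only.

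- SAP 6.2.6.1 defines the tablet total as a plain sum: "Cumulative DB exposure (tablets), derived by summing the number of tablets across records with complete dosing date and valid DB wallet number".
- The monthly average has two branches. The first is "Average DB exposure (tablets per month), derived as (1) cumulative DB exposure if time on DB study drug < 14 days, or". The second, from 14 days on, is "4 × cumulative DB exposure/time on DB study drug if time on DB study drug".
- Time on drug is counted inclusively: "Time on DBT (weeks), derived as (DBT end date DBT start date + 1)/7". Under SAP 7.1 the end date is that of the last tablet: "DB study drug end date: latest complete dose date from IP Administration DB or OL CRF records with number of tablets taken > 0".
- SAP 3.1 fixes the month: "A month is defined as 4 weeks (28 days) for the purpose of this protocol".
- SAP 6.2.6.2 places the average, by reference to 6.2.6.1, in rows cut at 11.2, 12.6, 15.4 and 16.8, described relative to EOD dosing, for example "> 15.4 (> 10% above EOD dosing". The table covers the safety analysis set, and no row or note exempts short exposure.
- In the same section, a worked example about taking at least 14 tablets glosses that count as "tablets (more than EOD frequency) per month for 3 consecutive months".

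SAP 6.2.6.1 uses the same two-branch rule for open-label (OL) exposure and for combined double-blind (DB) or OL exposure. It gives no reason for the rule.

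**The concern.** A count over a few days and a rate per 28 days are different quantities, yet both carry the same label and go into the same bands. The raw count presumably keeps very short exposures from being inflated, but it makes the band labels untrue for anyone with under 14 days on drug. Adherent subjects are pushed below the adherence rows, and daily users are kept out of the over-use rows. The exposure table has its own category for less than 2 weeks on drug, so the plan expects such subjects. At stake is whether the compliance table, the compliance listing and the exposure summary describe these subjects correctly.

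**Working it through.** **Reproducing the bands.** EOD dosing over 28 days is 28/2 = 14 tablets. Multiplying by 0.8, 0.9, 1.1 and 1.2 gives 11.2, 12.6, 15.4 and 16.8, exactly the SAP's cut-offs. The bands are therefore built on 14 tablets per 28 days.

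**Applying the rule.** For d days on drug and c tablets, the value is c if d < 14, and 4c/(d/7) if d ≥ 14. Because the end date is the last dose date, a perfect EOD user has an odd number of days and has taken (d + 1)/2 tablets. A daily user has taken d tablets.

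| Days | EOD tablets | SAP value | % of 14 | Daily tablets | SAP value | % of 14 |
|---|---|---|---|---|---|---|
| 1 | 1 | 1 | 7% | 1 | 1 | 7% |
| 7 | 4 | 4 | 29% | 7 | 7 | 50% |
| 11 | 6 | 6 | 43% | 11 | 11 | 79% |
| 12 | n/a | n/a | n/a | 12 | 12 | 86% |
| 13 | 7 | 7 | 50% | 13 | 13 | 93% |
| 14 | n/a | n/a | n/a | 14 | 28 | 200% |
| 15 | 8 | 14.93 | 107% | 15 | 28 | 200% |

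**Reading the table.**
- Perfect EOD use below 14 days never exceeds 7, so the 11.2 and 12.6 rows are out of reach. Two days later the same behaviour reads 4 × 8/(15/7) = 14.93.
- Daily use below 14 days never exceeds 13, so the 15.4 and 16.8 over-use rows are out of reach. It falls in the 10% band at 13 days, in the 20% band at 12 days, and under 80% at 11 days or fewer. At 14 days it jumps to 4 × 14/2 = 28.
- Scaled to 28 days, the two 13-day subjects have rates of 28 × 7/13 = 15.08 and 28 × 13/13 = 28.

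**Comparison with the table's other measure.** For an odd number of days n, SAP 6.2.6.2 sets the required tablets at n/2 + 1, which is 7.5 at n = 13. If the counting window ends at the last dose, tablet count compliance is 7/7.5 = 93% for the EOD subject and 13/7.5 = 173% for the daily subject. The EOD subject thus passes 80% on one measure and reads 50% on the other, within one table. The daily subject passes the 80% tablet-count row, which has no upper limit.

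**Would plain scaling cure it?** Not for very short use. 28c/d for perfect EOD dosing gives 28 at 1 day, 18.67 at 3 days, 16.8 at 5 and 15.56 at 9. It enters the 10% band only from 11 days (15.27).

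**The 14-tablet gloss.** Perfect EOD dosing gives 14 tablets in each 28-day interval, and the bands treat 14 as 100% of schedule. Describing 14 or more as above EOD frequency conflicts with that.

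**The case against.** The strongest reply is that the average is not the plan's main compliance measure. Tablet count compliance is a separate row, and it, not the average, defines the under-80% dosing deviation in SAP 9.1. More than one tablet on a day and any non-scheduled dosing day have their own rows, and the first is also a listed deviation. The study drug listing shows every dosing date. Table contents are partly deferred to a Core SAP that is not among the documents, so a footnote there cannot be ruled out.

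Most of this stands, and it limits the consequence. It does not remove the fault. The row for more than one tablet a day misses single daily tablets. The non-scheduled row depends on how sites label the extra days, and it gives no degree of over-use. The rows for three consecutive months cannot apply to someone with under 14 days on drug. The rate bands are therefore the table's only graded measure of over-use, and they fail for these subjects.

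Three stronger readings are tempting, and the documents do not support them:
- A reader might infer that every subject under 14 days reads 50% when adherent, or within 10% of schedule when doubling the dose frequency. Both figures belong to the 13-day case alone.
- A reader might infer a distortion of the tolerability assessment. Nothing in the documents links this average to any safety analysis.
- A reader might infer that adherent completers will be tabulated as over-users. The gloss sits inside a worked example, and the row itself is labelled only by its tablet count.

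The OL table is also a weaker case. Its categories carry no EOD-adherence labels, and OL dosing includes as-needed use. There the fault is confined to calling a raw count a monthly rate.

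**Conclusion.** The rule is wrong as written for DB exposure under 14 days. Perfect EOD adherence reads as 7% to 50% of schedule. Daily dosing reads as compliant at 12 or 13 days, as under-dosing before that, and as double the schedule from 14 days. The effect is limited to descriptive exposure and compliance output. Efficacy analyses and the under-80% tablet-count deviation do not use the value.

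The conclusion assumes that time on DB study drug is the inclusive count from first to last tablet defined in SAP 6.2.6.1 and 7.1, and that the Core SAP makes no exception. How many subjects are affected cannot be stated, because no rate of stopping before 14 days is given. Purely as an assumption, 2% to 5% of about 490 randomized would be roughly 10 to 25 subjects. That would count everyone with short exposure, not daily users near 13 days.

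The 14-tablet gloss is a separate, minor wording error.

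**What to change.** Take subjects with under 14 days on DB drug out of the EOD rate bands and show them in their own row, with tablets taken against tablets required for their days.

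Alternatively, for the DB bands at every duration, use 14 × tablets / EOD-required tablets over the same days, with required defined as days/2 rounded up. This gives 14 × 7/7 = 14 for perfect EOD use at 13 days and 14 × 13/7 = 26 for daily use. The rounding must be written out, because the SAP's odd-day formula read literally gives 14 × 7/7.5 = 13.07 for perfect use. This option largely restates tablet count compliance and reports a single tablet on day 1 as 14 per month, so the separate row is cleaner.

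In the OL and the combined DB-or-OL summaries, do not label the raw count as a monthly rate.

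In the worked example in SAP 6.2.6.2, reconcile the gloss with the bands by writing *at least EOD frequency*.

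The cost is SAP wording and one derivation. No new data are needed.

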2 STUDY DESCRIPTION

2.1 Study Design

This is a multicenter, randomized, double-blind, placebo-controlled study to assess the efficacy and safety of rimegepant in migraine prevention in Japanese subjects.

The study has 4 phases:

- Observation Phase (OP): Lasts approximately 28 days. Includes the Screening Visit and Prerandomization Evaluation Visit which must occur within 4 days of the Baseline Visit
- Double-blind Treatment (DBT) Phase:
 - Lasts up to 12 weeks, and includes the Baseline Visit, and Week 2, 4, 8, and 12/End of Treatment (EOT) Visits
 - Subjects are randomized 1:1 to one of the following 2 treatment groups at the Baseline Visit:
 - Rimegepant 75 mg dosed every other day (EOD)

- Placebo matching rimegepant 75 mg dosed EOD.
- Randomization is stratified by prophylactic migraine medication use (yes or no).
- Subjects are instructed that they can take a maximum of 1 orally disintegrating tablet (ODT) of double-blind (DB) study drug per every other calendar day.
- All randomized subjects who discontinue early from the DBT Phase should complete the EOT Visit. Otherwise, subjects should complete the Week 12 Visit.
- Open-label Extension (OLE) Phase:
 - Subjects who (1) complete the DBT Phase, (2) continue to meet all inclusion/exclusion criteria, and (3) have been compliant with the electronic diary (eDiary) may enter the OLE Phase, pending review of laboratory test results.
 - Lasts up to 40 weeks, and includes the Week 14, 16, 20, 24, 28, 32, 36, 40, 44, 48, 52/EOT Visits
 - Subjects are instructed that they can take a maximum of 1 open-label (OL) rimegepant 75 mg ODT (1) per every other calendar day on days they are scheduled to dose, and (2) as needed (pro re nata [PRN]) to treat a migraine on days they are not scheduled to dose.
 - All randomized subjects who discontinue early from the OLE Phase should complete the EOT Visit. Otherwise, subjects should complete the Week 52 Visit.
- Follow-up Phase:
 - Lasts up to 14 days and includes the Follow-up Week 2 Visit primarily for safety assessments. The Follow-up Week 2 Visit should occur approximately 2 weeks after the last visit in the last treatment phase (i.e., Week 12/EOT Visit if the subject did not enter the OLE Phase; Week 52/EOT Visit if the subject entered the OLE Phase).
 - All randomized subjects should complete the Follow-up Week 2 Visit, regardless of completing either treatment phase.

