4 ANALYSIS SETS, TREATMENT GROUPS, AND SUBGROUPS

4.1 Analysis Sets

The following analysis sets are used for statistical analyses, as applicable:

- Enrolled: subjects who signed informed consent and were assigned a subject identification number by the interactive web response system (IWRS), i.e., nonmissing informed consent date. This analysis set is used mainly to assess study population and in by-subject listings.
- Full: subjects in the enrolled analysis set who were assigned a randomized treatment group by IWRS, i.e., nonmissing IWRS randomization date. This analysis set is used mainly to assess study population.
- Safety: subjects in the enrolled analysis set who take ≥ 1 dose of study drug (DB or OL), i.e., nonmissing study drug start date. This analysis set is used to assess study population, exposure, and on-treatment safety, and produce select by-subject listings.
 - \circ DBT safety: subjects in the safety analysis set who take \geq 1 dose of DB study drug

(rimegepant or placebo), i.e., nonmissing DB study drug start date. This analysis set is used to assess study population, exposure, and on-DBT safety.

- \circ OL rimegepant safety: subjects in the safety analysis set who take ≥ 1 dose of OL rimegepant, i.e., nonmissing OL rimegepant start date. This analysis set is used to assess study population, exposure, and on-OL rimegepant safety.
 - Interim safety: subjects in the OL rimegepant safety analysis set with OL rimegepant start date – DB study drug last date > 7 days. This analysis set is used to assess post-DBT pre-OL rimegepant safety.
- DB or OL rimegepant safety: subjects in the safety analysis set who take ≥ 1 dose of DB or OL rimegepant, i.e., nonmissing DB or OL rimegepant start date. This analysis set is used to assess study population, exposure, and on-DB or OL rimegepant safety.
- Follow-up safety: subjects in the safety analysis set whose last contact date is in the followup safety analysis period. This analysis set is used to assess follow-up safety.
- DBT efficacy: subjects in the full analysis set who (1) are randomized only once, and (2) take
 ≥ 1 dose of DB study drug. This analysis set is used mainly to assess outcomes research
 endpoints during the DBT Phase.

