- Total DB exposure (tablets) summed across all subjects, derived by summing cumulative DB exposure across all subjects
- Total DB exposure (patient-years), derived by summing (DBT end date DBT start date + 1)/365.25 across all subjects.

OL Rimegepant Exposure

OL rimegepant exposure is provided descriptively by treatment group/OL rimegepant and overall for the OL rimegepant safety analysis set, and includes the following parameters:

- Time on OL rimegepant (weeks), derived as (OL rimegepant end date OL rimegepant start date + 1)/7
- Time on OL rimegepant (weeks) categories: $\leq 12, \leq 24, > 24$
- Time on OL rimegepant milestone categories:
 - $\circ \geq 3$ months, defined as ≥ 11 weeks
 - $\circ \geq 6$ months, defined as ≥ 23 weeks
- Cumulative OL rimegepant exposure (tablets), derived by summing the number of tablets across records with complete dosing date and valid OL wallet number
- Average OL rimegepant exposure (tablets per month), derived as (1) cumulative OL rimegepant exposure if time on OL rimegepant < 14 days, or (2) 4 × cumulative OL rimegepant exposure/time on OL rimegepant if time on OL rimegepant ≥ 14 days
- Total OL rimegepant exposure (tablets) summed across all subjects, derived by summing cumulative OL exposure across all subjects
- Total OL rimegepant exposure (patient-years), derived by summing (OL rimegepant end date OL rimegepant start date + 1)/365.25 across all subjects.

DB or OL Rimegepant Exposure

DB or OL rimegepant exposure is provided descriptively by treatment group/OL rimegepant and overall for the DB or OL rimegepant safety analysis set, and includes the following parameters:

- Time on DB or OL rimegepant (weeks), derived as (DB or OL rimegepant end date DB or OL rimegepant start date + 1)/7
- Time on DB or OL rimegepant (weeks) categories: $\leq 12, \leq 24, > 24$
- Time on DB or OL rimegepant milestone categories:
 - $\circ \geq 3$ months, defined as ≥ 11 weeks
 - $\circ \geq 6$ months, defined as ≥ 23 weeks
 - $\circ \geq 1$ year, defined as ≥ 51 weeks.
- Cumulative DB or OL rimegepant exposure (tablets), derived by summing the number of tablets across records with complete dosing date and valid DB rimegepant or OL rimegepant wallet number

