6.4.1.5 On-DB or OL Rimegepant AEs

Frequency tables of on-DB or OL rimegepant AEs by SOC and PT are provided for the DB or OL rimegepant safety analysis set for below endpoints:

- AEs by worst intensity (secondary objective #8)
- SAEs (secondary objective #8)
- Exposure-adjusted multiple occurrences of unique AEs.

Calculations for on-DB or OL rimegepant exposure-adjusted multiple occurrences of unique AEs use an analysis period reference start date = DB or OL rimegepant start date, analysis period reference end date = DB or OL rimegepant last date + 7 days if the DB or OL rimegepant last date is nonmissing, and analysis period reference end date = DB or OL rimegepant end date if the DB or OL rimegepant last date is missing.

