6.4.2.2 LFT Elevations

LFT Elevations

Frequency tables of LFT elevations are provided for the following safety analysis periods and analysis sets:

- On-DBT for the DBT safety analysis set
- Post-DBT pre-OL rimegepant for the interim safety analysis set
- On-OL rimegepant for the OL rimegepant safety analysis set
- On-DB or OL rimegepant for the DB or OL rimegepant safety analysis set
- Follow-up for the follow-up safety analysis set.

Results support exploratory objective #9.

LFT Shifts from Baseline to Worst Elevation

Frequency tables of LFT shifts from baseline to the worst (highest) LFT elevation are provided for the following safety analysis periods and analysis sets:

- On-DBT for the DBT safety analysis set
- On-OL rimegepant for the OL rimegepant safety analysis set.

Exposure-adjusted Cumulative LFT Elevations

Frequency tables of exposure-adjusted cumulative LFT elevations are provided for the following safety analysis periods and analysis sets:

• On-DB or OL rimegepant for the DB or OL rimegepant safety analysis set.

Calculations use the same analysis period reference start and end dates as corresponding exposure-adjusted AEs (see Section 6.4.1.5).

Time to First LFT Elevation

Frequency tables of time to first LFT elevation are provided for subjects with select LFT elevations (ALT > 3x ULN; AST > 3x ULN; ALT or AST > 3x ULN) for the following safety analysis periods and analysis sets:

- On-DB or OL rimegepant for the DB or OL rimegepant safety analysis set with on-DB or OL rimegepant LFT elevations
 - Time categories are: ≤ 2 , > 2 to ≤ 4 , > 4 to ≤ 8 , > 8 to ≤ 12 , > 12 to ≤ 16 , > 16 to ≤ 20 , > 20 to ≤ 24 , > 24 to ≤ 28 , > 28 to ≤ 32 , > 32 to ≤ 36 , > 36 to ≤ 40 , and > 40 weeks.
 - Time to elevation is calculated as (LFT collection date DB or OL rimegepant start date + 1)/7.

LFT Plots

Evaluation of drug-induced serious hepatotoxicity (eDISH) scatter plots are provided for the following safety analysis periods and analysis sets:

- On-DBT for the DBT safety analysis set by treatment group
- On-OL rimegepant for the OL rimegepant safety analysis set by treatment group/OL rimegepant.

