 - Before the final database lock: OL rimegepant end date derived only for subjects with "yes" or "no" response to the phase completion question on the OLE Subject Status or Follow-up Subject Status CRF
 - Final database lock: OL rimegepant end date

This is an analysis period reference date.

- DB or OL rimegepant start date: study drug start date for subjects whose as-treated DB treatment group is rimegepant; OL rimegepant start date for subjects whose as-treated DB treatment group is placebo. This is an analysis period reference date.
- DB or OL rimegepant end date: study drug end date for subjects whose as-treated DB treatment group is rimegepant; OL rimegepant end date for subjects whose as-treated DB treatment group is placebo
- DB or OL rimegepant last dose date: study drug last date for subjects whose as-treated DB treatment group is rimegepant; OL rimegepant last date for subjects whose as-treated DB treatment group is placebo. This is an analysis period reference date.
- OP start date: earliest of the following: screening visit date 1 day; eDiary efficacy date. This is an analysis period reference date.
- OP end date:
 - \circ If the study drug start date is nonmissing: study drug start date 1 day
 - If the study drug start date is missing and the randomization date is nonmissing: randomization date 1 day
 - \circ $\,$ If both study drug start date and randomization date are missing: last contact date

This is an analysis period reference date.

- Last contact date:
 - 1. Earliest complete death date from the AE CRF, if it exists.
 - 2. Otherwise, the latest complete date of the following: AE start or end; ECG; eDiary finding; informed consent; dose; IWRS randomization; laboratory test collection; non-study medication start or end; physical exam; physical measurement; procedure; rating scale; questionnaire; vital sign; visit.
 - 3. If the last contact date is after the most recent raw database creation date, then it is set to the most recent raw database creation date.
- Death date: refer to the Core SAP.

No imputations are performed on these derived dates unless otherwise specified.

Refer to the Core SAP for the definition of complete dates.

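### The SAP's combined time on double-blind or open-label rimegepant includes the drug-free gap between phases, but only for subjects whose as-treated double-blind group is rimegepant

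*SAP*

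**What the plan says.** SAP Section 6.2.6.1 defines the combined exposure time as "Time on DB or OL rimegepant (weeks), derived as (DB or OL rimegepant end date DB or OL rimegepant start date + 1)/7", read as end date minus start date. Patient-years use the same span divided by 365.25. The exposure milestones and average tablets per month are built on it too.

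Section 7.1 supplies the dates. For one group the rule is "DB or OL rimegepant start date: study drug start date for subjects whose as-treated DB treatment group is rimegepant". For the other it is "OL rimegepant start date for subjects whose as-treated DB treatment group is placebo". End dates follow the same split. The study drug start and end dates are the first and last dose on either the DB or the OL form, so for an as-treated rimegepant subject they run across both phases.

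The exposure-adjusted AE table (Section 6.4.1.5) uses the same start date and, when the last date is known, "analysis period reference end date = DB or OL rimegepant last date + 7 days". For exposure-adjusted LFT elevations, Section 6.4.2.2 states: "Calculations use the same analysis period reference start and end dates as corresponding exposure-adjusted AEs".

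The SAP expects that some subjects will have a gap. Section 2.1 says that subjects who complete DB treatment and qualify "may enter the OLE Phase, pending review of laboratory test results". Section 4.1 sets up an interim safety set for subjects whose OL start is more than 7 days after their last DB dose: "This analysis set is used to assess post-DBT pre-OL rimegepant safety". That period has its own AE overview and LFT tables.

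**The concern.** The combined span contains days on which the subject took no rimegepant and which the SAP reports separately elsewhere. The rule also acts on one side only. In the three-column layout of Table 4 (DB rimegepant/OL, DB placebo/OL, overall), the gap enters the first and third columns and never the second.

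These are the figures that describe long-term exposure. The one-year milestone, set at 51 weeks or more, is the most sensitive. The extension lasts up to 40 weeks, so on the planned schedule a placebo-first subject cannot reach it. The count comes essentially from the subjects whose gap is included.

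There is also an internal mismatch. The study drug listing shows time on DB treatment, time on OL rimegepant and the combined time for each subject. For a rimegepant-first subject with a gap, the first two do not add up to the third.

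**Working it through.** The SAP states no gap length, exposure total or rate, so there is no figure of its own to reproduce. The check traces the dates and then shows a range.

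**Inputs.** DB treatment up to 12 weeks = 84 days; extension up to 40 weeks = 280 days (Section 2.1). Every-other-day dosing, so 364/2 = 182 tablets over both phases. Safety window of 7 days after stopping (Section 3.2). Milestone of 51 weeks = 357 days (Section 6.2.6.1). The gap g, in drug-free days between last DB and first OL dose, is an assumption: 2 to 28 days.

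**1. Time on drug, as-treated rimegepant subject completing both phases.** SAP span = (84 + g + 280)/7 weeks. Without the gap = (84 + 280)/7 = 52.0 weeks. Tablets per 4 weeks = 4 × 182 / SAP span.

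| g (days) | SAP span (weeks) | Excess = g/364 | Tablets per month |
|---|---|---|---|
| 0 | 52.0 | 0 | 14.0 |
| 2 | 52.3 | +0.5% | 13.9 |
| 7 | 53.0 | +1.9% | 13.7 |
| 14 | 54.0 | +3.8% | 13.5 |
| 28 | 56.0 | +7.7% | 13.0 |

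Patient-years rise by the same percentage for each affected subject. A placebo-first completer has 280/7 = 40.0 weeks whatever the gap. The excess is proportionally larger when OL time is shorter: with 84 OL days the base is 168 days, and a 14-day gap adds 14/168 = 8.3%.

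**2. Milestone.** With a 7-day gap, 350 days on drug suffice (350 + 7 = 357), which is 50 weeks. With a 14-day gap, 357 − 14 = 343 days, or 49 weeks. With a 28-day gap, 357 − 28 = 329 days, or 47 weeks.

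**3. Person-time in the exposure-adjusted tables.** This is a different window, because it adds 7 days after the last dose. Counted = 84 + g + 280 + 7. Keeping at most 7 gap days, in line with the SAP's own safety window, gives 84 + min(g, 7) + 280 + 7.

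- g = 7: 378/378, no difference.
- g = 14: 385/378 = 1.019, or +1.9%.
- g = 28: 399/378 = 1.056, or +5.6%.

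**4. Effect on the rate.** Take the on-treatment event rate as 1 and let r be the event rate in gap days beyond day 7, relative to it.

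- Gap events not counted: relative rate = 378/385 = 0.982 (g = 14) or 378/399 = 0.947 (g = 28).
- Gap events counted: relative rate = (378 + r(g − 7))/(371 + g). For r = 0.5, 1 and 1.5 this gives 0.991, 1.000 and 1.009 at g = 14, and 0.974, 1.000 and 1.026 at g = 28.

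Person-time therefore grows in every case with g above 7, but the rate can fall, stay the same or rise.

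**The case against.** A reader might infer that the exposure-adjusted AE and LFT rates for rimegepant-first subjects must be understated. The documents do not support that. The safety analysis periods and the definition of exposure-adjusted AEs are left to the Core SAP, which is not among the documents. Section 6.4 also makes the gap a subdivision of the wider on-treatment safety period, so gap events may well be counted. If they are, numerator and denominator cover the same days. A reader might also take the split to be by randomized group; Section 7.1 uses as-treated group.

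Other points against have some force:

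- **No material gap is documented.** OLE Month 1 begins on study day 85, directly after DB day 84, and the wait for laboratory review has no stated length. A 28-day gap followed by 280 OL days would end on day 84 + 28 + 280 = 392, beyond the Week 52 window (days 351 to 378). With 280 OL days, that window leaves room for 378 − 364 = 14 days. The supplied protocol is for C4951022, a single-dose study without an extension, and the SAP is for C4951021, so entry procedures cannot be checked. This limits the size but not the derivation.
- **First-to-last-dose time is a convention**, and the SAP subtracts no missed doses in either phase. That is so, but this interruption is one the SAP names and tabulates separately, and the convention treats the two columns differently.
- **Gap-free totals can be recovered.** DB and OL patient-years are reported separately, cumulative tablets are unaffected, and the listing shows the dates. This helps with aggregate totals. It does not correct the milestone counts or the per-subject summaries.
- **The columns differ by design, and safety endpoints are not tested.** No inference is affected. The harm is descriptive.

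**Conclusion.** The point holds for exposure. For as-treated rimegepant subjects who enter the extension, the stated derivation counts the DB-to-OL gap as time on rimegepant; for as-treated placebo subjects it does not. Time on drug, patient-years and the 51-week count are overstated and tablets per month understated, in that column and in the overall column. The size depends on an assumed gap: over 84 + 280 days, from +0.5% (2 days) to +7.7% (28 days), and negligible if gaps are short.

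For the exposure-adjusted AE and LFT tables the supportable conclusion is narrower. Gap days beyond the 7-day window sit in the person-time (+1.9% at 14 days, +5.6% at 28 days). Rates are understated if gap events are left out of the numerator. If gap events are counted, the rates mix time on and off drug and may be lower, unchanged or higher. Gaps of up to 7 days cause no distortion by the SAP's own window.

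**What to change.** For as-treated rimegepant subjects who enter the extension, derive combined time as (DB end − DB start + 1) + (OL end − OL start + 1). Use it for weeks, patient-years, milestones and tablets per month. Where OL start falls on or before DB end, which Section 6.2.6.2 lists as a compliance category, keep the single span so that overlapping days are not counted twice.

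In the exposure-adjusted AE and LFT tables, remove the days from DB last date + 8 through OL start date − 1 from both person-time and events, and show those events in the interim tables. Keeping 7 days here but none in the exposure summaries is consistent with the SAP, which already ends exposure at the last dose and the safety window 7 days later.

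The cost is SAP wording and minor reprogramming with dates already derived. Patient-years and the one-year count become slightly lower. No new data are needed.
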